## Peripheral vascular disease

Term/Description	ICD10	ICD9CM	Read codes	ICPC
Peripheral Vascular Disease	I73.9	443.9, 443.81	G73y., G73z., Xa0IV, XE0VP, X203Q, Gyu74	K92
Atherosclerosis of arteries of the extremities	I70.2	440.20- 440.24 440.29		
Embolism and thrombosis of arteries of the upper extremities	I74.2	444.21		
Embolism and thrombosis of arteries of the lower extremities	I74.3	444.22	XaDtl	
Embolism and thrombosis of arteries of extremities, unspecified	I74.4	444.2		
Embolism and thrombosis of iliac artery	I74.5			
Peripheral angiopathy in diseases classified elsewhere	I79.2			
Insulin-dependent diabetes mellitus with peripheral circulatory complications *	E10.5	250.7		
Non-insulin-dependent diabetes mellitus with peripheral circulatory complications *	E11.5			
Bypass graft of the extremities *		440.3	XC0gN	
Chronic total occlusion of artery of the extremities *		440.4		
Diabetic ulcer lower extremities*		707.1		
Amputation due to diabetes*		785.4		
Embolism and thrombosis of an arm or leg artery			G742.00	
Peripheral arterial embolism and thrombosis NOS			G742z00	
H/O: Peripheral vascular disease procedure *			14NB.00	
Claudication distance			16I..00	
Percutaneous transluminal placement peripheral stent artery *			7A56600	
Diabetes mellitus with gangrene			C107.11	
Diabetes with gangrene			C107.12	
Diabetes mellitus, adult with gangrene			C107200	

Insulin dependent diabetes mellitus with gangrene			C108600	
Insulin dependent diab mell with peripheral angiopathy			C108G00	
Non-insulin dependent diabetes mellitus with gangrene			C109500	
Type II diabetes mellitus with gangrene			C109511	
Type 2 diabetes mellitus with gangrene			C109512	
Non-insulin-dependent d m with peripheral angiopathy			C109F00	
Type II diabetes mellitus with peripheral angiopathy			C109F11	
Type 2 diabetes mellitus with peripheral angiopathy			C109F12	
Type 1 diabetes mellitus with gangrene			C10E600	
Type 2 diabetes mellitus with gangrene			C10F500	
Type II diabetes mellitus with gangrene			C10F511	
Type 2 diabetes mellitus with peripheral angiopathy			C10FF00	
Type 2 diabetes mellitus with peripheral angiopathy			C10FF00	
Other peripheral vascular disease			G73..00	
Peripheral ischaemic vascular disease			G73..11	
Ischaemia of legs			G73..12	
Peripheral ischaemia			G73..13	
Peripheral gangrene			G732.00	
Gangrene of toe			G732000	
Gangrene of foot			G732100	
Gangrene of finger			G732200	
Gangrene of thumb			G732300	

Gangrene of hand			G732400	
Ischaemic foot			G733.00	
Other specified peripheral vascular disease			G73y.00	
Diabetic peripheral angiopathy			G73y000	
Peripheral angiopathic disease EC NOS			G73y100	
Other specified peripheral vascular disease NOS			G73yz00	
Peripheral vascular disease NOS			G73z.00	
Intermittent claudication			G73z000	
Claudication			G73z011	
Vascular claudication			G73z012	
Peripheral vascular disease NOS			G73zz00	
Ischaemic leg ulcer			M271.12	
Ischaemic ulcer diabetic foot			M271000	
Neuropathic diabetic ulcer - foot			M271100	
Mixed diabetic ulcer - foot			M271200	
Arterial leg ulcer			M271300	
Mixed venous and arterial leg ulcer			M271400	
[D]Gangrene of toe in diabetic			R054200	
[D]Widespread diabetic foot gangrene			R054300	

\* Not to be used for the identification of new (incident) events but just for the characterization of baseline patient characteristics (history of).

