### 9.2.5.3. Comparative safety study

Patients with any of the newly defined contra-indications will be excluded:

1. Established, current or past history of ischemic heart disease (IHD),
2. Peripheral arterial disease (PAD),
3. Cerebrovascular disease (CVD),
4. Uncontrolled hypertension, defined by MAH using an operational definition as follows: a patient will be defined as 'uncontrolled hypertension' if the 3 following conditions apply:
  - a. There is a previous diagnosis of hypertension coded in electronic medical records.
  - b. There is documented use of any anti-hypertensive therapy (either at that time or in the previous year before SR/BP initiation).
  - c. There are at least two readings of Systolic Blood Pressure  $\geq 150$  or Diastolic Blood Pressure  $\geq 95$  mmHg recorded in the 3 months prior to SR/BP initiation.

Also, eligible patients with a diagnosis of Paget's disease of bones will be excluded. And for the outcome VTE we will exclude patients with a previous VTE.

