### 9.3.2. Contra-indications and new indications

#### CONTRA-INDICATIONS

- History of Ischemic heart disease (IHD): myocardial infarction, angina pectoris, coronary artery bypass surgery (diagnoses or nitrate use) in year prior to SR therapy initiation.
- History of Peripheral arterial disease (PAD) in year prior to SR therapy initiation.
- History of transient ischemic attack (TIA) or stroke (ischemic or haemorrhagic) in year prior to SR therapy initiation.
- Uncontrolled hypertension, defined by MAH as the combination of the following: 1.previous diagnosis of hypertension coded in electronic medical records; 2.documented use of any anti-hypertensive therapy (either at that time or in the previous year before SR therapy initiation); and 3. at least two readings of Systolic Blood Pressure  $\geq 150$  or Diastolic Blood Pressure  $\geq 95$  mmHg recorded in the 3 months prior to SR therapy initiation.
- History of thromboembolic events (pulmonary embolism and deep venous thrombosis) in year prior to SR therapy initiation.

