**Figure (9.6) 1 - Model for data sharing and elaboration**

Due to the different database characteristics and coding schemes it is not possible to use one single data extraction algorithm for all the databases. To reconcile differences across terminologies a shared semantic foundation will be built for the definition of events under study by selecting disease concepts from the Unified Medical Language System (UMLS, V.2008AA), and set up a multi-step and iterative process for the harmonization of event data. The sequential steps of this process are shortly described below:

All events/outcomes and (contra)-indications will be ascertained using a list of agreed ICD (Denmark, Italy, and Spain), ICPC (Netherlands) and READ (UK) codes. The proposed lists of codes (See Appendix 14.3.2) were created following a number of steps:

1. Clinical definition;
2. Preliminary list of concept identifiers using UMLS Metathesaurus Browser;
3. Addition of codes found after literature review of validated lists of codes for each of the study outcomes in each of the databases; and
4. Consensus with academic partners involved in the management and analysis of each of the data sources. As coding might change over time, relevant codes might be updated during the course of the project. Harmonization of these code lists will take place between databases by comparison of population based age and sex specific incidence rates, according to standard quality assurance procedures in the EU-ADR Alliance (see below).

The sets of codes proposed in Appendix 14.3.2 will be further discussed with each of the academic partners during the first months of the study, and before data extraction.

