### 14.3.2. List of ICD-10, ICD-9, ICPC and READ codes used for the identification of key health outcomes and covariates.

The sets of codes proposed will be further discussed with each of the academic partners during the first months of the study, and before data extraction.

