#### Myocardial infarction / angina pectoris / aorto-coronary bypass surgery

Terms	ICD10 (SIDIAP, Aarhus hospital outpatients)	ICD9CM (HS, Aarhus hospital admissions)	Read Codes (THIN UK)	ICPC (IPCI)
Cardiac infarction	I22 I21			
MI - Myocardial infarction			X200E	
Acute myocardial infarction	I21		G30.. XE0Uh	K75
Acute myocardial infarction, unspecified	I21.9	410.9		
Myocardial infarction (acute) NOS	I21.3	410		
Acute myocardial infarction, unspecified site, episode of care unspecified		410.90		
AMI NOS, unspecified		410.90		
Acute myocardial infarction, subendocardial infarction		410.7	G32..	
Old myocardial infarction*	I25.2	412		
Healed myocardial infarction*			XE2aA G32.11	
Old myocardial infarction*			XE2aA	
Subsequent/recurrent myocardial infarction	I22		G35..	
Subsequent myocardial infarction of unspecified site	I22.9		Gyu36	
Subsequent myocardial infarction of other sites	I22.8		Gyu35 G353.	
Subsequent myocardial infarction of anterior wall	I22.0		G350. GYU3600	
Subsequent myocardial infarction of inferior wall	I22.1		G351.]	
Subsequent acute subendocardial myocardial infarction	I22.2			
Subsequent nontransmural myocardial infarction NOS	I22.2			
Subsequent myocardial infarction (acute) NOS	I22.9			
Reinfarction of myocardium			G35..	
Acute subendocardial myocardial infarction	I21.4		G307.00	
Acute myocardial infarction, subendocardial infarction, episode of care unspecified		410.70		

Terms	ICD10 (SIDIAP, Aarhus hospital outpatients)	ICD9CM (HS, Aarhus hospital admissions)	Read Codes (THIN UK)	ICPC (IPCI)
Nontransmural myocardial infarction	I21.4			
Acute myocardial infarction, of anterolateral wall		410.0	G300.	
Acute anteroseptal myocardial infarction			G3011	
Acute inferior myocardial infarction		410.4	X200K	
Acute myocardial infarction, true posterior wall infarction		410.6		
True posterior myocardial infarction			G306.	
Acute myocardial infarction, of inferoposterior wall		410.3	G303.]	
Other specified anterior myocardial infarction			G301.]	
Acute transmural myocardial infarction of unspecified site	I21.3		Gyu34	
Acute transmural myocardial infarction of anterior wall	I21.0 122.0			
Acute transmural myocardial infarction of inferior wall	I21.1 I21.11 I21.19 122.1			
Acute transmural myocardial infarction of other sites	I21.2 I21.21 I21.29 122.8			
ECG: old myocardial infarction*			3232.	
Anterior myocard.infarct NOS		410.8	G301z	
Other acute myocardial infarct			G30y.	
Other acute myocardial inf.NOS			G30yz	

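### The PAD code list counts a neuropathic foot ulcer (Read) and an unqualified diabetic lower-limb ulcer (ICD-9-CM) as arterial disease, with no ulcer row in the ICD-10 or ICPC columns

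*Protocol*

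**What the plan says.** Section 9.3.2 defines the contraindication as "History of Peripheral arterial disease (PAD) in year prior to SR therapy initiation". Section 9.2.5.3 applies it to the comparative study: "Patients with any of the newly defined contra-indications will be excluded". Section 9.6 says that contraindications are ascertained from agreed lists, using "ICD (Denmark, Italy, and Spain), ICPC (Netherlands) and READ (UK) codes".

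The only list in Section 14.3.2 that serves PAD is the peripheral vascular disease table. It has four code columns (ICD-10, ICD-9-CM, Read, ICPC). Two entries matter here:

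- Read M271100, "Neuropathic diabetic ulcer - foot", without an asterisk.
- ICD-9-CM 707.1, "Diabetic ulcer lower extremities", with an asterisk. The footnote explains the asterisk: "Not to be used for the identification of new (incident) events but just for the characterization of baseline patient characteristics (history of").

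The myocardial infarction table in the same section maps the ICD-9-CM column to "ICD9CM (HS, Aarhus hospital admissions"), whereas Table (9.4) 1 gives ICD-10 as the coding system for Aarhus. The introduction to Section 14.3.2 treats the lists as provisional: "The sets of codes proposed will be further discussed with each of the academic partners during the first months of the study".

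**The concern.** The contraindication is arterial disease, and one row of its code list names a cause that is not arterial. The Read ulcer rows are otherwise split by cause: ischaemic, arterial, or mixed. The neuropathic row does not fit that logic. Row 707.1 names diabetes and a site but no arterial disease, and no rule asks for a vascular diagnosis alongside it. Section 7.2 lists diabetes among the risk factors that call for caution rather than among the contraindications, and Section 9.3.4 labels it a precautionary condition. Scoring a diabetic ulcer with no arterial component as PAD blurs that distinction.

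Three planned outputs depend on the list: the prevalence of each contraindication by country (Section 9.7.2.2), the safety incidence rates by number of contraindications (Section 9.7.3.2), and eligibility for the comparative study (Section 9.2.5.3). Because the ICD-10 and ICPC columns have no ulcer row, the PAD concept also differs between databases.

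**Working it through.** No figure in the Protocol rests on these rows, so there is nothing to reproduce. The check is a reading of the table, a trace of one patient, and some bounding arithmetic.

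**1. Ulcer rows by column (Section 14.3.2, peripheral vascular disease)**

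| Column | Ulcer rows | Databases |
|---|---|---|
| Read | Ischaemic, arterial and mixed rows, plus neuropathic M271100 | THIN |
| ICD-9-CM | 707.1 (history only) | HSD; also Aarhus admissions by the header of the infarction table |
| ICD-10 | None | SIDIAP; Aarhus by Table (9.4) 1 |
| ICPC | None | IPCI |

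**2. Does the asterisk remove 707.1?** No. It bars use as an incident event. PAD is not a safety endpoint in Section 9.3.1 and is used only as baseline history, which is the use the footnote permits.

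**3. Trace of a patient.** Take a THIN patient whose only PAD-list code in the year before SR initiation is M271100, with no other contraindication. She enters the PAD numerator, moves from stratum 0 to stratum 1 in the incidence rates, and is excluded from the comparative study. The same ulcer in SIDIAP or IPCI matches no row, so there she is not PAD and stays eligible.

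**4. Reach, from 2012 incident SR users in Table (9.5) 1**

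- THIN: 514 / 5,819 = 8.8%
- HSD: 1,209 / 5,819 = 20.8%
- THIN + HSD: 1,723 / 5,819 = 29.6%
- Adding Aarhus (46): 1,769 / 5,819 = 30.4%

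These are all SR users in the databases that carry the codes, not affected patients. The row that is wrong by its own label (M271100) reaches THIN only.

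**5. Effect on prevalence.** Let a and b be the true PAD proportions in the reference and assessment periods, and f the share of users with an ulcer code and no other PAD-list code. Recorded prevalence is a + f, so the level is too high by f. The documents give no f. As an assumption, take f from 0.2% to 2%. Section 9.5.1 assumes a combined MI/CVD/PAD prevalence of 19.2% in women. Against that yardstick the relative shift is at most 0.2 / 19.2 = 1.0%, 0.5 / 19.2 = 2.6%, or 2 / 19.2 = 10.4%. It is at most this because ulcer patients with another contraindication are already counted in the composite. For PAD alone, the relative overstatement is f / a. With an assumed a of 3% this is 0.2 / 3 = 7% up to 2 / 3 = 67%, so it depends almost wholly on inputs that the documents do not supply.

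**6. Effect on the time series.** Section 9.7.2.2 fits segmented linear regression to monthly proportions and tests absolute level and slope. With constant f:

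(a + f) − (b + f) = a − b

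The change in level is the same at every f, and a constant adds nothing to a slope. Bias would need f to drift over time.

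**The case against.** The strongest reply has four parts. The lists are provisional. Section 9.6 accepts that one extraction algorithm cannot serve all databases. Section 9.6.4 benchmarks event and covariate rates and investigates outliers. Finally, 707.1 sits among other diabetic complication codes and can be read as a deliberate, broad history proxy. The last part has some force: 707.1 is debatable, while M271100 is wrong on its face. The first three do not remove either code. A modest excess of ulcer-only patients could also pass the benchmarking as ordinary variation between countries.

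A reader might infer four stronger claims, none of which the documents support.

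- *Only HSD and THIN are affected.* The header of the infarction table also gives the ICD-9-CM column to Aarhus admissions. This conflicts with Table (9.4) 1, so the set of affected databases is unsettled.
- *707.1 covers lower-limb ulcers of any cause.* That needs a code book outside the documents; the Protocol labels the row as diabetic.
- *The effect of the risk minimisation is materially diluted.* If true PAD fell from 3% to 1%, the relative fall would read 1 − 1.2/3.2 = 62.5% at f = 0.2%, or 1 − 3/5 = 40% at f = 2%, against a true 67%. But these inputs have no source in the Protocol, and the planned tests concern absolute level and slope, which a constant f leaves unchanged.
- *The safety comparison is biased.* The exclusion applies equally to SR and bisphosphonate starters, and controls are matched within data source. This narrows the population slightly; nothing shows a distorted odds ratio.

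**Conclusion.** The code list is wrong as written, with a probably small effect. M271100 does not belong in a PAD list, and 707.1 carries no arterial qualifier. The ICD-10 and ICPC columns have no counterpart to either.

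The consequences that stand are an upward shift in the recorded PAD prevalence level in the databases using these codes, some patients placed one contraindication stratum too high, and exclusions from the comparative study that depend on the coding system. Only patients whose sole PAD-list code in the look-back is one of these two are affected, and their number cannot be computed from the documents. The conclusion that the time-series level and slope changes are unbiased assumes that the ulcer share is constant over time.

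**What to change.** Before extraction:

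1. Delete M271100 from the PAD list.
2. Delete 707.1, or keep it only in a sensitivity analysis. Requiring a PAD code from the table alongside it amounts to deletion, because such a patient already counts as PAD.
3. Keep the ischaemic, arterial and mixed ulcer rows.
4. Apply the same PAD concept across the four code columns.
5. Reconcile the header of the infarction table with Table (9.4) 1 on how Aarhus is coded.

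The cost is a code-list edit at a point where Section 14.3.2 already schedules discussion with the academic partners. The downside is that a few true PAD patients recorded only by one of these ulcer codes would no longer be captured; the sensitivity analysis with 707.1 would show how much that matters for the ICD-9-CM data.

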## Pulmonary / deep vein thrombosis

Term/Description	ICD10	ICD9CM	Read codes	ICPC
Phlebitis and thrombophlebitis of femoral vein	I80.1			
Phlebitis and thrombophlebitis of other deep vessels of lower extremities	I80.2			K94.01 K94.15
Pulmonary embolism	I26			K93
Phlebitis and thrombophlebitis of deep vessels of lower extremities		451.1, 451.2**		
Acute venous embolism and thrombosis of deep vessels of lower extremity		453.4		
Pulmonary embolism and infarction		415.1		
Pulmonary embolism Pulmonary embolus Post operative pulmonary embolus Recurrent pulmonary embolism * Deep vein phlebitis and thrombophlebitis of the leg Deep vein thrombosis Deep vein thrombosis, leg DVT - Deep vein thrombosis Thrombophlebitis of the femoral vein Thrombophlebitis of the popliteal vein Thrombophlebitis of the anterior tibial vein Thrombophlebitis of the posterior tibial vein Deep vein thrombophlebitis of the leg unspecified Deep vein thrombosis of leg related to air travel Deep vein thrombosis of lower limb Deep vein thrombosis of leg related to intravenous drug use Deep vein thrombosis of peroneal vein Deep vein phlebitis and thrombophlebitis of the leg NOS Thrombosis of vein of leg  Post operative deep vein thrombosis [V] Personal history deep vein thrombosis * [V] Personal history DVT- deep vein thrombosis * [V] Personal history of pulmonary embolism * Thromboembolic pulmonary hypertension *			G401.00 G401.12 G401000  G401100 G801.00  G801.11 G801.12 G801.13 G801600  G801700  G801800  G801A00  G801B00  G801C00  G801D00  G801E00  G801F00  G801z00   G802000  SP12200  ZV12800	

			ZV12811 ZV12900 G41y100	
Personal history of pulmonary embolism		V12.55		
Personal history of venous thrombosis and embolism		V12.51		
Iliac vein thrombosis/embolism			G08Y	

*\* Not to be used for the identification of new (incident) events but just for the characterization of baseline patient characteristics (history of).*

*\*\* Code to be used for HSD data only following suggestion from co-investigators.*

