### 9.2.2. Study Period

The study period will start on January 1st 2004 (year of licensing) for all databases except January 1st 2006 for SIDIAP (as data is only available from 2005, and a 1-year washout is required) and will end at the most recent version of data that is available with each of the database custodians.

The study period will be divided into three analysis periods for the assessment of RMM effectiveness: up to May 2013 (*reference* period before first DHPC and revised SmPC), between June 2013 and March 2014 (*transitional* period), and after April 2014 (*assessment* period after second DHPC and new SmPC revision).

As for the safety studies, the study period will be divided in two analysis periods: 1. up to May 2013 (when the first DHPC was published, imposing new contraindications), and 2. from June 2013 (when patients with any of the new contraindications should not be prescribed SR any longer) onwards.

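### In SIDIAP the exclusion of previous VTE has no ICD-10 history code to work with, so VTE that predates the record or is noted only as history is missed; any bias in the VTE odds ratio is probably modest and depends on unproven channelling

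*Protocol*

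**What the plan says.** - **Exclusion.** Protocol 9.2.5.3 states: "for the outcome VTE we will exclude patients with a previous VTE". It gives no look-back. Section 9.3.2, which defines the contraindications, counts thromboembolic history only in the year before SR is started.
- **VTE code list (Appendix 14.3.2, Pulmonary / deep vein thrombosis).** The ICD-9-CM column has V12.51 ("Personal history of venous thrombosis and embolism") and V12.55 for pulmonary embolism. The READ column has ZV12800, ZV12811 and ZV12900. The ICD-10 column has only I80.1 ("Phlebitis and thrombophlebitis of femoral vein"), I80.2 and I26. The ICPC column has only K93, K94.01 and K94.15.
- **Other lists in the same appendix.** ICD-10 codes for past disease are given for "Old myocardial infarction" (I25.2), bypass surgery (Z95.1) and stroke sequelae (I69.x).
- **Asterisk rule.** An asterisk bars a code from identifying new events. The READ personal-history VTE terms carry it, and so does V12.54 in the stroke list. V12.51 and V12.55 do not.
- **SIDIAP.** Its study period starts in 2006, "as data is only available from 2005, and a 1-year washout is required" (9.2.2). Table (9.4) 1 gives its disease coding as ICD-10.

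**The concern.** A case is a first occurrence after cohort entry (9.3.1). If a patient's earlier VTE is not visible, that patient stays in the cohort treated as having no previous VTE, and a recurrence counts as a first event. The VTE risk of SR was already recognised before the 2013 measures (7.2). It is therefore plausible that prescribers gave patients with past VTE a bisphosphonate instead. High-risk patients would then collect in the reference group and push the SR odds ratio down, against a trial relative risk of only 1.5 (7.2). The exclusion would also be more complete in some databases than in others, although the estimates are to be pooled (9.7.4).

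**Working it through.** **1. Share of SR users in SIDIAP (Table (9.5) 1, incident users 2012).** The column sum reproduces the stated total: 1,209 + 4,008 + 514 + 46 + 42 = 5,819.
- SIDIAP: 4,008 / 5,819 = 68.9%.
- SIDIAP, Aarhus and IPCI together: 4,096 / 5,819 = 70.4%. SIDIAP is 4,008 / 4,096 = 98% of these.
- Aarhus (46, 0.8%) is also assigned to the ICD-9-CM column for hospital admissions, in the header of the infarction list. IPCI (42, 0.7%) has free text (9.4.1), which 9.6.1 plans to search.

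The gap therefore lies essentially in SIDIAP.

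**2. What is missed there.** The event codes I26, I80.1 and I80.2 are not limited to outcomes, so a VTE coded in the record before entry is found. Two kinds are not: a VTE before the record begins, and one noted only as history. With data from 2005, a patient entering in January 2006 has about one year of record, and one entering in May 2013 can have about eight. The gap shrinks with entry date.

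**3. Possible size of the bias.** The protocol gives no VTE history by drug, so every input here is an assumption. Let h be the share of starters with a missed earlier VTE and r their VTE rate relative to other patients. Each group's rate is inflated by 1 + h(r − 1), so

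factor on the odds ratio = [1 + h_SR(r − 1)] / [1 + h_BP(r − 1)].

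| h_BP | h_SR | r = 4 | r = 8 |
|---|---|---|---|
| 1% | 0.25% | 1.0075/1.03 = 0.98 | 1.0175/1.07 = 0.95 |
| 2% | 0.5% | 1.015/1.06 = 0.96 | 1.035/1.14 = 0.91 |
| 3% | 1% | 1.03/1.09 = 0.94 | 1.07/1.21 = 0.88 |
| equal | equal | 1.00 | 1.00 |

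In the middle row a true 1.5 is read as 1.44 to 1.36 within SIDIAP.

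**4. Pooled.** If SIDIAP holds 68.9% of both drug groups (also assumed; the protocol has no such figure for bisphosphonates) and nothing is missed elsewhere, multiply each h by 0.689:
- r = 4: (1 + 0.689 × 0.015) / (1 + 0.689 × 0.06) = 1.0103/1.0413 = 0.97
- r = 8: (1 + 0.689 × 0.035) / (1 + 0.689 × 0.14) = 1.0241/1.0965 = 0.93

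A true 1.5 is then read as 1.46 to 1.40.

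**5. Look-back.** If the one-year definition of 9.3.2 also governs 9.2.5.3, an event-coded VTE older than one year would stay in as well, in every database. The two sections have to be reconciled before the yield of any history code is defined.

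**The case against.** The case on the other side has force.

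- **The list is provisional.** Sections 9.6 and 14.3.2 leave the codes open for discussion before extraction. That is true, but nothing there flags this gap, and that discussion is the moment to close it.
- **SIDIAP can already be set apart.** Estimates are made by database before pooling (9.7.4), and a sensitivity analysis without Spain is planned (9.7.5). This would show a difference between SIDIAP and the rest. It does not replace a repair, because it drops about 69% of incident SR users.
- **VTE cases are validated.** A sample is checked in each source, in SIDIAP against hospital admissions (9.3.1). This helps against an old event that is re-recorded. It confirms that an event is real, not that it is the first, so true recurrences pass.
- **Prior anticoagulant use is a candidate confounder (9.3.4).** It could absorb part of the bias. But 9.9 adjusts only for covariates that change the estimate by 10%, and the middle scenario lies below that.
- **The ICPC gap is not specific to VTE.** The infarction, stroke and peripheral lists have no ICPC history code either. Nor do the documents show that usable ICD-10 or ICPC history terms for VTE are recorded in these databases. This stands, and the fix is worded accordingly.

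A reader might infer that the exclusion fails throughout the ICD-10 and ICPC databases, so that 70% of SR users are affected. The documents do not support this: the event codes still work, and 70.4% is where SR users are located, not the share with a missed VTE. A reader might also infer that the missed patients are mainly bisphosphonate users. That is reasoning from the recognised risk; no figure in the protocol shows it.

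**Conclusion.** The point holds for SIDIAP. The VTE list lacks an ICD-10 history term although the same appendix supplies such terms for infarction, bypass and stroke. The exclusion of previous VTE is therefore less complete in the database that holds 68.9% of 2012 incident SR users. What is missed is limited to VTE before the record or noted only as history. A downward bias in the SR odds ratio follows only if past-VTE patients were steered away from SR. Under the assumptions shown it is modest: a factor of 0.96 to 0.91 in SIDIAP and about 0.97 to 0.93 pooled, and 1.00 if missed history is equally common in both groups. Even then, the exclusion differs between databases that are to be pooled.

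Two further faults bear on the same codes. The look-back is unstated in 9.2.5.3 and one year in 9.3.2. And V12.51 and V12.55 lack the asterisk, so in HSD (1,209 / 5,819 = 20.8% of incident SR users) a history code could count as a new VTE. The change is worth making before extraction.

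**What to change.** 1. Add baseline-only (asterisked) VTE-history terms for ICD-10, and for ICPC or IPCI free text where they exist.
2. State in 9.2.5.3 that previous VTE is searched in all data available before cohort entry, and reconcile this with the one-year definition in 9.3.2.
3. Put the asterisk on V12.51 and V12.55.
4. Report the prevalence of VTE history by drug and database. This replaces the channelling assumption with data, at least for recorded history.
5. Add a sensitivity analysis of the VTE outcome without patients who used an anticoagulant in the year before cohort entry, a variable that 9.3.4 already extracts.

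The cost is a code-list edit, a sentence on look-back, one table and one extra analysis. Non-specific history terms and the anticoagulant restriction will also remove some patients without past VTE, so there will be slightly fewer patients and VTE cases.
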